## Off label and investigational use of drugs/devices

Choose from the following that will be applicable to your study

✓ Drug

Select the number of drugs used in this study

1

## Drug #1

Name of the drug

Ketamine Hydrochloride

Manufacturer and other information

The pharmacy at PI will be supplying the drug.

Approval Status

IND is approved

IND#

110,464

Who holds the IND/IND sponsor?

IND is held by PI/CU Investigator

[name]

## Research Related Delay to Treatment

Will research procedures result in a delay to treatment?

Yes

Maximum duration of delay to any treatment

The screening process should take about a week, after which eligible participants will be consented and provided MET, an effective psychotherapy for cannabis use disorders. Ineligible participants will be referred to appropriate treatment. Thus, the maximum duration of delay to treatment is about a week.

Maximum duration of delay to standard care or treatment of known efficacy

MET and MBRP are evidence-based behavioral treatments for cannabis use disorders that are provided to all consenting participants after they complete the screening process. The maximum delay to standard treatment is therefore about a week.

Treatment to be provided at the end of the study

All participants will be referred to appropriate evidence-based treatment for substance use disorders, including 12-step groups, further psychotherapy, addiction psychiatry, or outpatient rehabilitation, depending on the individual's needs and preferences.

## Clinical Treatment Alternatives

Clinical treatment alternatives

Participants not interested in entering this trial will be referred to appropriate treatment for cannabis dependence, such as 12-step groups or outpatient/inpatient rehabilitation.

## Risks/Discomforts/Inconveniences

Risks that could be encountered during the study period

The major risk of research participation is related to ketamine administration. Other risks include intravenous line placement.

Pregnant and lactating women are especially at risk as the medications used can be harmful to a fetus or newborn child as well as the mother herself.

Describe procedures for minimizing risks

1) Ketamine: The dose of ketamine employed in this study was specifically selected because it is equivalent

to the dose used with therapeutic effect in other settings, and comparable to doses that have been used safely in substance users (alcohol, cannabis, cocaine, opioids) in different protocols at this facility (Protocols 6162, 6176, 7014, 7051, 7057). Ketamine at the dose used in this study may be associated with a wide spectrum of psychological, perceptual and physiological effects. The psychological and perceptual effects include depersonalization, derealization, word-finding difficulties, slowed cognition, anxiety, agitation, confusion, and sensory changes. Physiological effects at the high dose include dizziness, blurred vision, and nausea. Additional side effects of ketamine that are more prominent at higher doses include tachycardia, increased blood pressure, sedation, analgesia, incoordination, jaw clenching, transient rash, increased perspiration, nystagmus, and fatigue. These effects tend to resolve immediately after the infusion is stopped. Participants are informed that they may stop the infusion and/or withdraw from the study at any time. A sitter will be present to address any distress that may emerge. In case of outpatient administration, participants will be closely monitored post-infusion to assess for persistent effects, and participants will only be discharged after 3 hrs have elapsed post-infusion and they have passed medical/psychiatric clearance and a field sobriety test.

The sitter, an ACLS certified physician, will also monitor for any side effects. Nausea and vomiting will be treated supportively and, if severe, with anti-emetic agents. So as to reduce the risk of nausea, vomiting, and aspiration, participants will be NPO after midnight prior to infusions. Anxiety and agitation will also be treated supportively and with relaxation exercises. If these side effects do not remit with such measures, and/or if the participant persists in asking that the session be stopped, the administration of ketamine will be discontinued. In other studies utilizing comparable doses of ketamine infusion, anxiety, psychosis and perceptual changes have always spontaneously resolved within 30 minutes of terminating the infusion, often within 5 minutes. Intramuscular preparations of midazolam and/or thiothixene will be kept available at the central pharmacy in order to rapidly control a ketamine-induced level of emotional distress, psychosis, or delirium should it persist. Any participant requiring pharmacotherapy to control a psychiatric complication of drug administration will be removed from the study, kept overnight for observation, and given referrals, if necessary, the next day, assuming the person can be safely discharged from hospital.

The administration of subanesthetic ketamine IV also induces a modest rise in vital signs. During the ketamine infusion, vital signs (blood pressure and heart rate) will be monitored every five minutes beginning five minutes before the infusion begins, and will be monitored after the infusion until baseline vital signs are restored. If  $HR > (220 - \text{patient age}) \times 0.85$  BPM, and if systolic blood pressure increases by  $> 60$  mm or diastolic blood pressure increases by  $> 40$  mm (or  $SBP > 200$  and  $DBP > 115$ ) during the ketamine infusion, the infusion will be permanently discontinued. The blood pressure and heart rate will be monitored and if there is no decrease after 5 minutes, then nitroglycerin, clonidine, or propranolol will be administered. If high blood pressure is symptomatic, i.e., blurred vision, headache, chest pain, the subject will be transferred to the ER.

Any medical risks from increased blood pressure will be minimized through the careful screening of potential subjects. Subjects will be excluded for baseline hypertension or any history of cardiovascular illness. In addition, an ACLS certified physician will be present during the procedure. Continuous ECG monitoring and pregnancy testing will be provided, as well.

Extensive laboratory experience suggests that sub-anesthetic ketamine generally produces transient effects without any persistent changes, but there are some data suggesting that ketamine, and glutamate modulators in general, may alter the glutaminergic system in such a way as to render vulnerable subjects more likely to

develop psychotic disorders. Previous studies, therefore, have tended to exclude participants with a personal or family history of psychosis in order to reduce the psychiatric risks that ketamine may pose. Accordingly, individuals with a personal or first-degree family history of psychosis will be excluded from this study. Furthermore, the protocol involves close monitoring and an assessment of psychiatric stability prior to discharge; this both ensures that any lingering sedation is allowed to dissipate, and that participants are closely monitored for persistent side effects. Participants will be screened by a psychiatrist and cleared for continued participation following the infusion on Week 2, Day 2, and they will also be followed twice weekly during the following phase of the trial. Subjects will be provided a number to call to reach an on-call psychiatrist (24 hours/day) should unpleasant effects occur after subjects have left the testing facility.

Ketamine is also associated with some abuse liability, though this abuse liability is significantly lower than that of other drugs of abuse, such as cannabis, cocaine, nicotine, alcohol, benzodiazepines, or opioids. Ketamine is generally insufflated, ingested, or injected intramuscularly in the community, and is often used in combination with other substances such as gamma-hydroxy-butyrate (GHB) or 3,4-Methylenedioxymethamphetamine (ecstasy). There is a risk, therefore, that participants may seek out ketamine after becoming exposed to it, and develop problematic patterns of ketamine use during or after the study. This risk may be compounded by the fact that it is given in this study to individuals who may have an increased vulnerability to developing substance use problems in light of their dependence on cannabis. While this important risk cannot be removed entirely, various safeguards can be implemented to ensure that it is minimized, including: 1) exercising “a minor deception” and giving participants the impression that they may receive any of a number of medications during each infusion, while ensuring that the side effects and risks are clearly conveyed; this may prevent patients from identifying ketamine and subsequently seeking it out; 2) excluding participants with a history of ketamine misuse or abuse; and 3) carefully monitoring drug use to ensure that any emergent patterns of misuse or abuse of ketamine, or any other substance, is properly addressed in a timely manner. Furthermore, ketamine is administered in this study in a way that is unrepresentative of how it is commonly used in the community (slow-drip IV infusion). In addition, this slow, sustained method of administration is unlikely to lead to the acute powerful effects generally associated with heightened abuse liability.

Participants who develop a significant adverse reaction during or after the infusion (psychosis, agitation, or adverse psychological response that is persistent and/or requiring pharmacotherapy; blood pressure elevation requiring termination) will lead to the blind being broken. This will alert the participant to his or her propensity for an adverse response to the drug, thus ensuring future safety.

There is a risk of adverse interactions with the study medications if participants are actively intoxicated on illicit medications. In order to minimize this risk, participants are encouraged to remain abstinent before the infusion, and will be tested daily with urine toxicology. They will also undergo a field sobriety test on the day of the infusion, prior to administration. In addition, they will be evaluated by a clinician ([name]) for DSM-IV signs of any intoxication.

In conclusion, the careful evaluation of participants during the screening process for cardiovascular, psychiatric, medical, and historical vulnerabilities to ketamine infusion; the presence of a psychiatrist with ACLS certification (the PI) during and after the infusion who will monitor for side effects and adverse events; the sub-anesthetic, generally well-tolerated dose at which ketamine will be infused; the close monitoring during infusion; the psychiatric evaluation and clearance to go home; the regular outpatient visits to monitor for persistent effects; and the provision of supportive and pharmacological measures to

address any side effects all ensure that the medical and psychiatric risks involved in participation in this study will be minimal.

2. Blood drawing/Intravenous placement: Another risk in the study is that bruising or a blood clot could form at the site of the intravenous line or venipuncture. Medical staff with extensive experience with IV placement will remain available to ensure that risks are minimized.

In order to safeguard against risks towards pregnant women, evaluation will be conducted on whether the risk of treatment is acceptable for women of childbearing potential. Staff will discuss with participants the risks associated with participation and the importance of adequate birth control practice. In addition, staff will evaluate whether the participant is willing and reliable to practice effective birth control during the study. Urine pregnancy testing will be conducted at baseline evaluation and on a weekly basis throughout the course of the study. Staff will periodically discuss with patients to review importance of not becoming pregnant, and adequacy of birth control practices (all of which will be documented). As the testing methods used have limitations, participants will be encouraged to inform the research staff if they believe they have become pregnant so that the safety of the participant can be ensured. As the risk towards pregnant women outweighs the benefits of participating in this study, if a participant becomes pregnant during the course of the study, they will be discontinued from their participation.

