## Background, Significance and Rationale

### Background, Significance and Rationale

This proposal will focus on treating cannabis use disorders with a one or two sub-anesthetic infusions of ketamine (0.11 mg/kg 2-min bolus followed by 0.6 mg/kg over 50 minutes or 1.3 mg/kg over 90 minutes), a high-affinity non-competitive N-methyl-D-aspartate receptor (NMDAR) antagonist. Our preliminary research suggests that ketamine improves dependence-related vulnerabilities common to a variety of substances. We have shown that a single infusion improves motivation to quit, reduces cue-induced craving, improves non-reactivity, and reduces cocaine self-administration among non-treatment cocaine dependent individuals. We have also shown that ketamine infusions can be integrated into outpatient behavioral treatment, such as motivational enhancement therapy (MET) and mindfulness-based relapse prevention (MBRP), to address cocaine use disorder and alcohol use disorder. This includes a protocol with cocaine users that provides up to 2 ketamine infusions. In these protocols, some individuals who had been using cannabis problematically in addition to the substance for which they sought treatment stopped using cannabis.

In this single blind, open label trial, we extend the treatment model we have developed to treat cocaine use disorder to the treatment of cannabis use disorder, with the expectation that we will observe similar feasibility. This protocol includes a manualized sequence of MET and MBRP in conjunction with up to 2 infusions of ketamine. The primary outcome is tolerability of study medications.

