## Specific Aims and Hypotheses

### Specific Aims and Hypotheses

The primary purpose of this study is to assess whether giving one or two sub-anesthetic dose of ketamine to cannabis users will be feasible.

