## Criteria for Early Discontinuation

### Criteria for Early Discontinuation

Patients may elect to drop out at any time, and they may be removed by the treating clinicians for clinical reasons, including 1) clinically significant worsening leading to an acute psychiatric emergency (e.g., suicidality, psychosis, mania), or **2 or more weeks of moderately significant worsening (ascertained by a clinical evaluation following 2 weeks of a score of at least 6 or 7 on the CGI improvement scale. A score of 6 or 7 would lead to a clinical evaluation and then clinical judgment as to whether the patient should be discontinued);** 2) **inability to comply with study procedures prior to to the 1st infusion;** or 3) medical complications of treatment. Patients who terminate due to medical or psychiatric problems will be offered the necessary level of care (e.g., psychiatric hospitalization for psychosis, inpatient detoxification and rehabilitation for worsening drug use). **Due to the risks to pregnant women and their unborn children associated with these medications, becoming pregnant would result in a participant's early discontinuation from the study.**

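### Removing a participant from the study after drug treatment for a psychiatric reaction ends collection of that reaction's later course, although tolerability is the primary outcome

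*Protocol*

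**What the plan says.** Background, Significance and Rationale sets the outcome: "The primary outcome is tolerability of study medications". Specific Aims and Hypotheses frames the trial as a feasibility study: "The primary purpose of this study is to assess whether giving one or two sub-anesthetic dose of ketamine to cannabis users will be feasible".

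Risks/Discomforts/Inconveniences sets the removal rule: "Any participant requiring pharmacotherapy to control a psychiatric complication of drug administration will be removed from the study". The participant is then "kept overnight for observation, and given referrals, if necessary, the next day, assuming the person can be safely discharged from hospital". For blood pressure and heart rate reactions the same section stops less: "the infusion will be permanently discontinued". Removal from the study is not mentioned there.

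Criteria for Early Discontinuation is discretionary. It says of patients that "they may be removed by the treating clinicians for clinical reasons", which include acute psychiatric emergencies and medical complications. Those who terminate are offered care, but no continued assessment is described.

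The safety argument in Risks/Discomforts/Inconveniences rests partly on later contact. After the first infusion participants are cleared for continued participation, and "they will also be followed twice weekly during the following phase of the trial". The concluding summary of safeguards lists "the regular outpatient visits to monitor for persistent effects".

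Under Assessment Instruments, the Adverse Symptom Report records presence, onset and resolution of adverse effects at study visits.

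**The concern.** Adverse effects and their resolution are collected at visits. Removal from the study ends the visits, and here it is triggered by a poor result on the primary outcome. The later course is therefore missing because of the outcome itself, in an uncontrolled trial of about 15 people where each such case carries weight.

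The affected participants are also those whose later course is least predictable. The protocol says that in studies at comparable doses, anxiety, psychosis and perceptual changes always resolved spontaneously within 30 minutes of stopping the infusion. It keeps rescue medication for reactions that persist. A participant who needs it is therefore, on the protocol's own account, outside that earlier experience. The protocol also cites data that ketamine may make vulnerable people more likely to develop psychotic disorders.

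A related gap concerns later ketamine use. The protocol names three safeguards: disguising the drug, excluding people with prior misuse, and monitoring drug use. A reaction requiring pharmacotherapy breaks the blind, and removal ends the study's monitoring. Two of the three safeguards then lapse in the same person.

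**Working it through.** **1. Does any section keep a removed participant in follow-up?**

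- Risks/Discomforts/Inconveniences: overnight observation, referral if necessary, discharge. No later study assessment.
- Criteria for Early Discontinuation: the necessary level of care is offered. No later study assessment.
- Study Procedures and Assessment Instruments: adverse effects are queried at visits.
- The 24-hour telephone number is a clinical contact that the participant must initiate. It is not scheduled data collection.

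None does. The haemodynamic rule shows that the protocol can stop an infusion without ending participation.

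**2. What is captured before removal?** A physician is present at the infusion. The CADSS follows it, and the BPRS positive-symptom items are scheduled for the same visit. Adverse symptoms are recorded, and the participant is observed overnight. The index event and its acute course are therefore observable.

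**3. What is lost?** The schedule's columns are 1, 2A, 2B, 2C, 3A, 3B, 3C, 4, 5, 6 and E (taken as the end-of-study assessment). In the machine-read table the CGI and Safety rows are one cell short at the left. Shifted one cell to match the other rows, each has 9 marks, from 2B to E.

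- Removal at the first infusion (2B): 2C, 3A, 3B, 3C, 4, 5, 6, E = 8 of 9 columns lost.
- Removal at the second infusion (3B): 3C, 4, 5, 6, E = 5 columns lost.
- Without the shift the rows run from 2A to 6, and the losses are 7 (2C to 6) and 4 (3C to 6). The original table should be checked.

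Columns are not visits: weeks 4, 5 and 6 have one column each but two treatment visits a week. The DES is marked only at 2C and 3C, so a participant removed at 2B has no post-infusion DES.

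**4. How many participants?** The protocol has no power or precision calculation to reproduce. Its only sample-size figures are 15 completers and 20 enrolled. They are consistent with an implied 25% non-completion: 1 − 15/20 = 0.25, and 15/(1 − 0.25) = 20.

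The rate of psychiatric rescue is not given. Assume a per-participant rate p between 2% and 15%. The expected number is np, and the chance of at least one case is 1 − (1 − p)^n.

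| Assumed p | Expected, n = 15 | At least one, n = 15 | Expected, n = 20 | At least one, n = 20 |
|---|---|---|---|---|
| 2% | 0.3 | 26% | 0.4 | 33% |
| 5% | 0.75 | 54% | 1 | 64% |
| 10% | 1.5 | 79% | 2 | 88% |
| 15% | 2.25 | 91% | 3 | 96% |

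The n = 20 columns assume that all enrolled participants are infused, so they are an upper bound. The plausible outcome is between none and about three participants.

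**The case against.** A reader might infer four stronger things. The documents do not support them.

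- **That the worst reactions go unrecorded.** They do not. The event, the rescue and the acute course occur under observation before removal.
- **That the tolerability rate will look better than it was, because removed participants drop out of the denominator.** No section says that tolerability is summarised in completers. The 15 completers are an enrolment target, not an analysis set, and a statistical analysis plan that is not shown may count everyone infused.
- **That everyone who tolerates ketamine badly is removed.** Mandatory removal covers only psychiatric reactions needing drug treatment. Haemodynamic reactions stop the infusion, and removal by the treating clinicians for psychiatric or medical reasons is discretionary.
- **That removed participants are left without care.** Overnight observation, discharge only if safe, referral, the offer of the necessary level of care and a 24-hour line are all provided.

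It can also be said that twice-weekly follow-up is described for participants cleared to continue, so there is no flat contradiction with removing others. That is fair. It can be added that few or no participants may need rescue, which is also fair.

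What remains is narrow. Clinical care is not outcome collection. An analysis plan can choose a denominator, but it cannot recover visits that the protocol ends.

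**Conclusion.** The point holds in this limited form. As written, the protocol ends research follow-up for participants who need pharmacotherapy for a psychiatric complication of the infusion. The course of a primary-outcome event after overnight observation is then not collected.

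The loss is up to 8 scheduled Safety columns per participant after the first infusion and 5 after the second. This rests on the realigned Safety row and on the second infusion taking place at 3B. Elsewhere the protocol allows it in week 4; the columns after that week are then 5, 6 and E. The number of participants is unknown and may be zero.

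No stated figure or analysis is wrong, and no bias in a reported rate is shown. The protocol should be amended because the missing data bear on the primary outcome and cannot be obtained later.

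**What to change.** Leave the clinical rules on rescue, stopping an infusion and removal by clinicians as they are, and change only what happens to data collection.

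1. In Risks/Discomforts/Inconveniences, distinguish the end of study infusions from the end of study follow-up. Do the same in Criteria for Early Discontinuation for participants removed for psychiatric or medical reasons.
2. State that such participants, if they agree, stay in the already scheduled Safety/adverse-symptom, CGI and physician visits to the end of the study. The physician visit already documents self-reported substance use, so later ketamine use would be covered.
3. Report tolerability over all participants who started an infusion. If an analysis plan already says this, a cross-reference is enough.

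The cost is an amendment to two sections, a line in the consent form and a few visits for a few people. The visits are on the schedule, but the protocol does not say that they are funded for removed participants. Some may decline, so follow-up will be better but not necessarily complete.
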